COVER PAGE

Date: 2-25-20

Study Protocol

: NCT03655470

Brief Title: Safety Planning in Juvenile Justice for Suicidal Youth

Official Title: Screening and Brief Intervention for Suicidality and Nonsuicidal Self-Injury Among Youth in the Juvenile Justice System

Secondary IDs: 1R34MH114307-01A1 [U.S. NIH Grant/Contract Award Number]

The proposed study will be divided into two phases. In Phase I, we will conduct an open trial with 10 adolescents which will allow us to make any modifications necessary for using the protocol in Probation. We will then randomize 60 suicidal JJ youth who screen positive for recent SI into standard care or the safety planning intervention. We will train two part-time counselors who have a master's degree in the mental health field and work in the local community mental health clinic, Gateway, in which MPI [name] and Co-I [name] have consulted. Counselors with community mental health experience were selected because youth in the JJS are typically served by community mental health clinics, so this choice was also made with an eye toward eventual implementation. In addition, the model proposed here – of mental health counselors embedded in Probation – is consistent with a co-responder model, found across the U.S. in which a PO works collaboratively with a mental health professional to coordinate care. Thus, if the protocol is found to be effective, there is an existing infrastructure that could aid further implementation. We will hire a bilingual counselors so they will be able to conduct the intervention and give feedback to youth and parents who are Spanish-speaking.

The counselors will cover afternoon appointments in Probation and be employed by the research grant because Probation rules prohibit audiotaping sessions with youth. By employing the mental health counselors on the grant, we will be able to rate tapes of sessions for fidelity and competency (see below). In order to conduct the study under conditions most relevant to a future implementation trial, we will also employ a training approach that has been successfully implemented by Co-I [name] with Bachelors and Masters level staff in a psychiatric hospital (see below)..

In Phase II, of the study, we will: a) conduct qualitative interviews in Probation about attitudes toward the intervention as well as barriers to a future, larger implementation trial; and b) conduct a **SIM Mapping**, described above, to outline a series of other potential “points of interception” along the JJS continuum, beyond Probation, where screening and brief intervention might be implemented in a future system-wide trial.

### **Phase I. Open trial and RCT**

**Study overview.** In this treatment development grant, 70 adolescents in Probation will be recruited to participate in the study. The first 10 will participate in an iterative development open trial. Then 60 youth will be randomized to: 1) the screening/brief intervention safety planning intervention, or 2) standard practice.

**Open Trial Design.** A total of 10 youth will be recruited for open trial in order to: a) test the protocol's applicability in Probation, and b) train the mental health counselors in the protocol. We have used this 2 phase approach extensively in prior studies. The open trial will occur in months 5 - 8 after counselor training. The protocol and procedures will be modified as necessary after the first 5 participants and then again after 10 pilots have been run through the protocol and prior to conducting the pilot RCT

[figure not shown]
**Overview of RCT Trial Procedures.** When youth arrive for their first Probation appointment, they are asked to complete the MAYSI/NSSI assessment. Youth who flag in on the MAYSI or NSSI item on this first screen, will be referred by their PO to the mental health counselor who will approach them about participation in the study. If the parent/caregiver consents to the study, the mental health counselor will then meet with the youth, physically separate from the parent/caregiver, to describe study procedures in detail (**including the fact that only youth who are positive on the secondary screen continue in the study**) and obtain juvenile assent without parental presence (see **Human Subjects**). Consenting procedures will also include permission to access court records. All youth will then complete the complete the Self-Injurious Thoughts and Behaviors Interview 2.0 (SITBI-Short Form^91, see below), to more thoroughly assess self-injurious behavior. Families will then be referred back to their PO to complete the secondary screen. If the youth screens in, he/she is then randomized to either standard practice or the safety planning intervention.

Follow-up assessments will also be completed at 1- and 3-months post-baseline to gather data on youth outcomes related to treatment, self-harm, and recidivism. No juvenile will ever be sanctioned by the court for not agreeing or being unable to participate in the research study (see **Human Subjects/Letter of Support**).

**Current standard practice.** The MAYSI-2 provides two cut-off scores: caution (2 items endorsed) and warning (3 or more items endorsed). (Note: a screening item from the SITBI – “Have you ever had thoughts of purposely hurting yourself without wanting to die, e.g. cutting, burning? If yes, how many separate times in your life?” – has also just been added as part of standard practice). If a teen has a positive screen for suicide risk, the PO completes a “secondary screener” built into the MAYSI- 2 to determine whether there is concern of current and/or imminent risk. If a teen endorses NSSI more than once in the prior year, then the PO asks about frequency and severity. If there is ongoing concern of risk for self-injurious behavior, then the PO arranges for a crisis evaluation in the Emergency Department (ED). If the teen is not judged to be at imminent risk, the PO makes a referral back to the current treatment provider or to a community mental health clinic. In either case, the parents and youth receive a packet with mental health resources.

In the experimental condition, if a teen screens positive on the secondary screener, and is randomized to

*the safety planning intervention, the PO will refer the case to the mental health counselor. The mental health counselor will conduct the safety planning intervention (described below) and then make a decision whether*

*the teen remains at imminent risk, and needs to be referred for an ED evaluation. If there is no imminent risk, the PO and mental health counselor together facilitate a referral back to the current treatment provider or to a community mental health clinic. The mental health counselor will also conduct a follow-up phone call one week after the safety plan to answer any questions about the safety plan and promote linkage to treatment as needed.*

**Participants.** Youth offenders, ages 12-17 will be eligible for enrollment with the following criteria: 1) Legal guardian available to consent for juvenile's participation, 2) Juvenile and parents are English or Spanish speaking; and 3) Juvenile flags in on the MAYSI-2 or NSSI item. *In order to maximize the ecological validity of this pilot trial, there will not be any exclusion criteria.* **Racial and Ethnic Minority**

**Considerations.** Consistent with 2016 RIFC statistics, ethnic representation will be approximately 18% Hispanic and racial

representation will be about 22% Africa American or Black (and other) and 72% White. **Estimated Sample Size and Retention Rates.** In 2016, the RIFC handled offenses for 2,634 juveniles of whom 764 (29%) were female and 2,581 (98%) who were in the 12-17 year old age range. The Juvenile Intake Department, for example, screens more than 904 juveniles per year and, of those youth who are screened, approximately 10% (N=89) flag for recent SI. In 2015, the detention center admitted 470 youth. *Probation had a caseload of 375 in 2015. Of these youth, it is estimated that 20% of youth screen positive for current risk of self-injurious behavior (N=75). Even with a conservative acceptance rate of 60%, we would be able to recruit about 45 youth per year and meet our 20 month projected enrollment goal of 60 participants, i.e. about 3 per month (3 x 20 = 60). Using a conservative follow-up rate of 80% (see **Retention**) of the 60 enrolled and retained participants, approximately 48 are expected to complete the 3-month follow-up.* This approach is feasible given our excellent working relationship with the JJS, including the RIFC, and prior experience recruiting from the juvenile intake department (see RIFC Chief Judge and Probation Letters of Support). MPI [name] collaborated on a 24-month longitudinal epidemiological study of first-time CINI offenders at the RIFC and we successfully recruited the entire sample of 400 first-time offending CINI youth (DA034538). MPI [name] is also currently recruiting at the RIFC juvenile intake department for a baseline sample of suicidal CINI youth for her NIMH K23 Mentored Career Award. MPI [name] also successfully established a referral system from RIFC to his NIAAA (AA017659) and NIDA (DA0029871) trials for youth with substance use-related court involvement.

**Experimental protocol: Safety Planning.** This brief intervention, consists of an in-person and follow-up phone call that are based on cognitive behavioral principles designed to help identify a concrete list of coping strategies and social supports that youth can utilize preceding or during a crisis to lower imminent risk of NSSI or suicidal behavior. Specifically, the Safety Plan will help the youth and caregiver identify: environmental risk factors including access to means and triggers; individualized warning signs; specific coping skills; peer and family social supports to help distract from negative thoughts; adult contacts for help; and reasons for living. The Safety Plan is also reviewed with parents and any barriers to the plan are discussed. For example, logistical barriers related to locking up medication may be problem solved or the family may discuss supportive ways the parent can respond if the teen reaches out for help. *In youth who also report NSSI, the safety plan format is suitable to address both suicidal and nonsuicidal behavior.* (Note: in a recent study, on which MPI [name] was an author, NSSI was found to be a stronger predictor of future suicidal behavior than even a prior suicide attempt). Safety planning has been determined to be a best practice by the Suicide Prevention Resource Center/American Foundation for Suicide Prevention Best Practices Registry for Suicide Prevention ([www.sprc.org](http://www.sprc.org)). The plan helps youth and parents identify possible triggers to including suicidal and self-injurious thoughts, feelings, and behaviors; develop a plan to remove lethal means; determine distress tolerance/emotion regulation skills that may be helpful; identify accessible social supports to target hopelessness/sense of isolation; reinforce the commitment to seek treatment; and reviews how and where to access emergency care. (See **Appendix 1** for safety plan worksheet).

[figure not shown]
If a juvenile flags in and is in the experimental condition, the safety planning will occur in three stages: 1) the juvenile will meet with a trained mental health counselor to create the safety plan; 2) the juvenile and counselor will meet with the PO and caregiver to share the safety plan and discuss strategies and challenges to implementing the safety plan; and 3) the PO will then contact the current mental health provider or appropriate community mental health clinic to facilitate an outpatient appointment, if the youth is not at immediate risk. In cases where substance use is an issue, the JJS staff member will ask permission of the youth to relay this to the community mental health clinic or current provider.

The Safety Plan intervention, *which consists of the one module from Co-I [name]'s COPES program described above*, incorporate the SITBI responses, which covers both suicidal and nonsuicidal ideation and behavior, to ensure all areas are covered in the Safety Planning process. For example, the SITBI will identify suicide means youth have thought about using. Youth make a list of dangerous items to remove from their surroundings (e.g., alcohol, knives, razors, medications) in order to reduce access to means, identify their warning signs and vulnerabilities that indicate they may become unsafe, generate helpful coping strategies, and identify people that can help them manage negative feelings.

*The safety plan intervention concludes with a section emphasizing completing referrals for outpatient care for those youth. Youth will also complete the 8-item Motivation for Youth's Treatment Scale (MYTS) to facilitate discussion between the counselor and the youth about the youth's current motivation for treatment. At the same time, the caregiver will complete the Barriers to Treatment Participation Scale (BTPS) that will inform the mental health counselor about potential barriers (identified as "often a problem" or "always a problem") and promote discussion during the safety planning with the youth and caregiver about those potentials barriers and generate ideas on how to overcome them.*

**Brief Intervention Follow-up Phone Call.** One week after the in-person safety planning, the mental health counselor will contact the teen's parent/caregiver to review elements of the safety plan and problem-solve barriers to using the safety plan and engaging in treatment. If the family has not made contact with a treatment provider, the mental health counselor will further assist the family in setting up an appointment. Co-I

[name]'s research with recently incarcerated and suicidal individuals has shown that telephone follow-up intervention is feasible, acceptable, and powerful in building trust and reducing risk among these populations.

**Baseline and Follow-up Assessment.** In order to pilot test a procedure with the greatest potential to be implemented in a large effectiveness trial in the future, we collect all baseline data from information collected routinely and recorded in court records, with the exception of administering the SITBI. Therefore, potential participants will not be paid for the completion of the baseline measures. The consent form will specify that, as part of participating in the study, the MPIs will be allowed to use the baseline data from the RIFC chart.

The follow-up assessment battery was also designed to reduce participant burden and will be scheduled at 1 and 3 months post-intervention. The 3-month follow-up period will allow us to assess a high-risk period for self-injury as well as the typical period of time that adolescents remain in outpatient psychotherapy. Follow up interviews will be conducted in-person and last approximately 1 hour. Juveniles and a caregiver will each be compensated \$30 for the time to complete the 1 and 3-month assessment.

**Protection against Attrition.** We do not anticipate a great deal of attrition at the 1 and 3-month follow-up assessment, based on our prior success in following participants in our other treatment studies. Nonetheless, after the baseline assessment, participants will be educated on the importance of completing the follow-up assessments; provided the date and time of the follow-up appointments, and provided a study contact number to call if contact information changes. Detailed tracking information will be recorded. Our retention strategies will include phone, texting, email, and postal mail contact (e.g., personalized holiday, thank you, and birthday cards). In addition, names of two friends or family members will be requested in the event that research staff is

unable to reach the participant using the above information. Participants will be asked to sign a letter addressed to each of their locators that explains that they are participating in a research project. Locators will be contacted only if all efforts to reach the patient have failed. Weekly case review meetings will review no-shows, non-verified and non-confirmed cases and activities necessary to ensure successful completion of the follow-up assessments. We have used these procedures with success in other projects. Participants will be contacted 1 week prior to each follow-up appointment. The phone-based follow-ups will assist with retention. In MPI [name]'s NIAAA-funded study with CINI youth, retention rates were 94% at 3 months and 84% at 6 months.

**Training in Assessment.** Training in the follow-up assessment protocol will occur during the first 3 months. Similar to the other JJS-involved protocols for MPI [name]'s other NIH-funded RCT projects, a primary bachelor's level research assistant (RA) will be trained to administer and score the assessment protocol for 1 and 3-month follow-ups. Under MPI [name]'s oversight, the RA will receive training on working in the JJS and on how to appropriately respond to logistical questions that participants' may have.

**Procedures for MH Deterioration/Safety Concerns.** It is possible that some participants will report symptoms that may warrant additional mental health care. POs routinely refer to community mental health clinics, as part of standard procedure, youth with any other emotional/behavioral problems in addition to self-injury. Our research team has conducted a number of studies involving assessment of self-injury (e.g. MH095786, MH090147, MH082211) and, as such, has developed procedures for managing self-injury when necessary at follow-up interviews (detailed in Human Subjects and **Appendix 2**).

**Phase I Measures (see Appendix 3).** The selection of measures was designed to be realistic for the JJS with an emphasis on eventual implementation in a larger effectiveness trial. The measures below will be collected electronically or by paper and pencil, if necessary, when there is limited internet access in Probation or on home visits.

#### **Background variables (obtained at baseline only).**

Standard demographic variables including age, sex, race, ethnicity, and education will be recorded from court records. (note: at the follow-up, youth will be asked questions about their gender identity because it is not currently asked in Probation). Legal history will also be obtained (available to study staff) as will item-level responses for the MAYSI-2 and NSSI screening data. The collection of data from legal records and existing JJS procedures is an additional strength of this service-based application as it improves feasibility and the potential for scalability.

#### **Youth level outcomes**

Feasibility of a future larger trial, will be defined as the percent of at-risk youth who enroll in the research project. Feasibility of conducting safety planning in Probation will be assessed by the percentage who receive the brief intervention, including linkage to treatment and the follow-up phone call, in total and in part.

Acceptability will be assessed by post-intervention ratings on the Client Satisfaction Questionnaire [CSQ-8;120], a well-established 8-item self-report instrument on a 4-point scale used to assess patients' satisfaction with psychiatric treatment. A score above 24 is the benchmark based on previous research. An "exit interview" will also be conducted at the one month follow-up about the intervention protocol that they received.

The Self-Injurious Thoughts and Behaviors Interview 2.0 (SITBI 2.0) Short Form^91 is a structured interview designed to assess the presence, frequency, and characteristics of a broad array of self-injurious thoughts and behaviors. The SITBI has good reliability and validity. The SITBI will be completed at baseline and 1 and 3-month follow-up to assess suicidal ideation, attempts, and NSSI. Suicidal events will be operationalized as a composite score of suicide attempts and emergency interventions for acute suicidality assessed by the CASA (see below). Recidivism (collateral data from RIFC database) including new arrests, description of related charges (e.g., substance-related, property) and time detained/incarcerated (all tracked by the RIFC database) will be available.

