#### **Youth level mechanisms**

Treatment Attendance (self-report, parent/caregiver report, and collateral information). The Child and Adolescent Services Assessment [CASA] is a self-and parent-report instrument designed to assess at follow-up the use of mental health services for youth across 31 settings including inpatient, outpatient, and informal services. The measure has acceptable psychometric properties. Collateral information on treatment attendance (attendance at first treatment appointment and total number of treatment sessions attended) will also be collected by contacting each juveniles' treatment provider at the 3-month follow-up. A release of information is requested at baseline, for both primary care physicians (PCP) and their MH provider/agency, as part of the court intake process when treatment referrals are made. The Motivation for Youth's Treatment Scale, an 8-item measure, will be used to assess the youth's motivation to engage in treatment at baseline and at follow-up. The total scale and two subscales (Problem Recognition and the Treatment Readiness) produce alpha coefficients of above .80. The baseline MYTS will be completed at the end of the safety planning intervention to screen and address youth and caregiver motivation for treatment. The Barriers to

Treatment Participation Scale, a 44-item measure, will be completed at baseline and 3-month follow-up by caregivers to assess barriers that parents/caregivers experienced since intervention and the role those barriers may play in treatment engagement. Alpha coefficients range from 0.61 to 0.80. Treatment Satisfaction information will be gathered as part of the follow-up qualitative interview. Youth and caregivers will be interviewed about their satisfaction with the suicide intervention as well as treatment referral in the community at the 3-month follow-up.

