*Performance of CT Strategies (PCTS) will be used to assess safety planning skills because it is more ecologically valid than a self-report measure. Raters will assess the extent to which participants demonstrated, through their performance of, their reports of the use of, and their stated intentions to continue the use of, safety planning skills based on a prompt to discuss what behaviors they did and continue to do to keep themselves safe. For example, "Did the youth understand and utilize restriction to means; individualized warning signs; specific coping skills; peer and family social supports to help distract from negative thoughts; adult contacts for help; and reasons for living". Each of the areas will be rated on a 0 to 6 Likert-type scale. Ratings of 4 or higher are considered indicative of independent use of the domain assessed by each item (i.e., clear report of the patient's making use of this domain). Three raters, blind to condition, will rate session tapes. Meetings of the entire rating group and pairs of raters will occur periodically to minimize rater drift.*

*We will also specifically ask teens and parents regarding the teen's access to potential means, including firearms, medications (over-the-counter and prescribed), and alcohol.*

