### **Phase I: Data Analysis Plan**

Prior to conducting analyses for the project aims, a series of routine procedures will be conducted to ensure the data accuracy/adequacy. All forms will be checked for missing data and all data will be double entered and backed-up daily. Descriptive statistics will be examined for distributional properties of the variables (e.g., normality, internal consistency). The data will be transformed to achieve normality if needed.

We will conduct analyses in an intent-to-treat (as randomized) manner, and examine as primary analyses unadjusted and secondarily adjusted for selected covariates identified above. Masking integrity will be reviewed. ANCOVA (outcome regressed on baseline) methods will be used, and linear mixed effect models will be used to account for non-independence of repeatedly observed outcomes.

We will examine attrition by comparing follow-up assessment completers and non-completers on socio-demographic and baseline data to determine if they differ systematically. Consistent with an intent-to-treat model, we will include all randomized participants in the analyses. Attrition/Missing Data. It is anticipated that less than 20% of subjects will not have follow-up data. We will test for differential attrition across the experimental condition and the baseline comparison. The analyses described below can account for attrition at the follow-up points. We will employ multiple imputation as our primary approach to missing data [138] and will conduct a sensitivity analysis treating all participants lost to follow-up as treatment failures at the point of loss, i.e. assuming no change on their self-injury-related mechanisms or outcomes. If our primary conclusions are similar with and without extreme missing data assumptions, confidence in the findings will be higher.

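### Does the plan need to mask the follow-up SITBI interviewer and put the SITBI ahead of the exit and satisfaction questions?

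*Combined protocol and SAP*

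**What the plan says.** - **Assessor.** Under Training in Assessment, a primary research assistant "will be trained to administer and score the assessment protocol for 1 and 3-month follow-ups". Nothing there mentions masking.
- **Visit.** Under Baseline and Follow-up Assessment: "Follow up interviews will be conducted in-person and last approximately 1 hour". No order of instruments is given. Under Phase I Measures: "The measures below will be collected electronically or by paper and pencil, if necessary".
- **SITBI.** Youth level outcomes describes it as a structured interview given at baseline, 1 month and 3 months. Primary Aim makes its ideation and attempts/NSSI results the main clinical outcomes. A separate composite draws on a second instrument: "Suicidal events will be operationalized as a composite score of suicide attempts and emergency interventions for acute suicidality assessed by the CASA".
- **Questions that could reveal the arm.** At month 1 an exit interview "will also be conducted at the one month follow-up about the intervention protocol that they received". At month 3 youths and caregivers are asked about "satisfaction with the suicide intervention as well as treatment referral in the community at the 3-month follow-up". The CSQ-8 is given after the intervention, with no visit named.
- **Masking.** For the skills measure (PCTS): "Three raters, blind to condition, will rate session tapes". The Phase I: Data Analysis Plan adds "Masking integrity will be reviewed", without saying whose.
- **Use of the data.** Primary Aim is feasibility and acceptability. For clinical outcomes it seeks standard deviations and pre-post correlations and disclaims a preliminary effect-size estimate. The Data Analysis Plan nevertheless tests the arms against each other, with main inference pooled over the two follow-ups.

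**The concern.** An interviewer who knows the arm can probe more or less, or code a borderline answer differently. Here the main clinical outcomes come from an interview, and the same visits contain questions about the care received. If the research assistant asks those questions too, the month-3 SITBI is scored by someone who heard the arm at month 1. The month-1 SITBI is exposed as well if it comes later in that visit.

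The only people called blind are the tape raters, so the masking review may not reach the SITBI assessor at all. At stake is the between-arm comparison of self-injury outcomes: a shift caused by the assessor would look like a treatment effect. Asking the SITBI first appears to be a protection that costs almost nothing.

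**Working it through.** **1. What must be true for harm.**

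| Step needed | What the supplied text says |
|---|---|
| The research assistant runs the exit or satisfaction interview | Interviewer not named |
| At month 1 the SITBI follows the revealing questions, or the same person returns at month 3 | Order not stated; the assistant is called primary, not sole |
| Knowing the arm shifts the recorded answers | Not addressed; the SITBI is structured and asks about presence and frequency |
| No masking was intended for this person | Not stated; the masking-review sentence shows that some masking was intended |

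The plan refers to Human Subjects and to Appendix 3 for measures. Neither is in the supplied text, and either could settle staffing or order.

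**2. Size if every step held.** The plan gives no figure for assessor bias, so there is none to reproduce. What follows illustrates assumptions.

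Inputs: 48 expected completers (Estimated Sample Size and Retention Rates), split 1:1 by assumption, so 24 per arm; correlation between repeated measures .64 (Power); no true effect; two-sided 5% test on the equally weighted mean of the two visits; assumed shift s = 0.1, 0.2 or 0.3 SD.

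- Standard error of the pooled difference, in SD units: √[(2/24) × (1 + .64)/2] = √.0683 = .261.
- Pooled shift = s(1 + k)/2, where k is the share of the shift present at month 1. The noncentrality is this divided by .261. For s = 0.3 and k = 1 it is .3/.261 = 1.15.
- False-positive rates from the noncentral t with 46 degrees of freedom:

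| Visits affected | s = 0.1 | s = 0.2 | s = 0.3 |
|---|---|---|---|
| Both (k = 1) | 6.6% | 11.6% | 20.3% |
| Month 3 in full, half at month 1 (k = .5) | 5.9% | 8.7% | 13.5% |
| Month 3 only (k = 0) | 5.4% | 6.6% | 8.7% |

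- With all 60 analysed (30 per arm) and s = 0.3, the three rates are 24.3%, 15.7% and 9.7%.
- The 95% half-width at 24 per arm is 2.013 × .261 = .526 SD, wider than any shift assumed.

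Binary attempts/NSSI at one visit, true risk assumed 30% in both arms, Pearson chi-square by full enumeration: if 10%, 20% or 30% of positives in one arm are coded negative, the apparent difference is 3, 6 or 9 points. The false-positive rate is then 5.8%, 7.8% or 11.3%, against 5.2% with no miscoding.

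**3. What the pilot's own goals would lose.** Enrollment, completion, withdrawal and satisfaction do not use the SITBI. A constant shift in one arm leaves within-arm standard deviations and pre-post correlations of a continuous score unchanged. A binary outcome is not fully immune: at the extreme of 30% missed, the recorded risk falls from .30 to .21 and that arm's SD from √(.30 × .70) = .458 to √(.21 × .79) = .407.

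**4. What each remedy would buy.**

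- *SITBI first.* This secures month 1. If the same person then asks anything revealing, month 3 is open whatever its order. That is the k = 0 row: better than k = 1, but not masked. It also puts the most sensitive interview before rapport is built.
- *Self-completed exit questions.* The exit interview sits with the acceptability measures, so thinner answers cost the primary aim in order to protect a secondary comparison. The CASA, the skills prompt and the means-access questions could still reveal the arm. Handing the interview to other staff needs people the documents do not identify; using the tape raters would endanger their blinding.
- *An arm-guess item.* With 48 guesses, percent correct is known to ±1.96 × √(.25/48) = ±14 points, and to ±1.96 × √(.25/24) = ±20 points within an arm. With no decision rule attached, no conclusion would change.

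**The case for a change.** The best case for a change accepts the pilot setting. The plan does test SITBI outcomes between arms and calls the pooled tests its main inferences. If they are to be reported, an inexpensive protection is reasonable. A pilot is also the place to settle visit order and assessor masking for a definitive trial. The illustrative gap between 20.3% and 8.7% at 0.3 SD is not trivial. Events that surface later in the visit need not be lost: dated corrections could be allowed, and emergency interventions recorded on the CASA already count in the composite.

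The factual part stands: the supplied text neither calls the assessor masked nor sets an order. Asking the SITBI first at month 1 is a sensible option for the team. What does not stand is that the plan must change. The 0.3 SD is assumed, the route to it is inferred, and order alone does not protect the pooled test. Youths also know what they received, so their own reporting bias remains under any order. The costs are real too: rapport, less informative exit answers, a Spanish self-complete version, and electronic or mailed forms for follow-ups done by phone.

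**Conclusion.** No change follows. This is an unwritten operational detail, not a rule that produces a wrong result. The plan intends some masking and does not say whom it covers. Staff can give the SITBI early in the visit if they judge it workable, and the report can state who gave it and whether that person knew the arm. That is documentation and alters no analysis.

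If assessor bias existed, it would affect the exploratory between-arm comparison. Under assumed shifts of 0.1 to 0.3 SD the pooled false-positive rate would be 6.6% to 20.3% with both visits affected, and 5.4% to 8.7% with month 3 alone. These figures rest on 24 per arm, a correlation of .64, 1:1 allocation and bias sizes with no source in the documents. The feasibility and acceptability targets are untouched, as are the SDs and correlations of continuous scores under a constant shift. The conclusion would need another look if the measures appendix or the Human Subjects section showed that the SITBI assessor is routinely told the arm, or if the between-arm tests were later put forward as evidence of efficacy.
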